## **4.3. End of Study Definition**

A subject will have completed the study if the final visit at Week 2/Visit 7 is completed or if the subject dies or is otherwise lost to follow-up.

The end of the study is defined as the completion of the final assessment for the last subject enrolled in the study.

---

## 5. STUDY POPULATION

Prospective approval of protocol deviations in recruitment and enrollment criteria, also known as protocol waivers or exemptions, is not permitted.

### 5.1. Inclusion Criteria

To be eligible to participate in the study, at the Screening Visit each subject must:

1. Be adequately informed and understand the nature and risks of the study and must be able to provide a signature and date on the informed consent form (ICF).
2. Be at least 18 and no more than 80 years of age at the Screening Visit. Subjects may be male or female.
3. Have known or evident liver cirrhosis. Diagnosis of liver cirrhosis may be based on clinical, radiological, and or histological criteria, including 1 or more of the following:
  - a. Liver biopsy (documented by histology);
  - b. Clinical evidence of cirrhosis, defined as aspartate aminotransferase greater than alanine aminotransferase, platelet count less than 150,000  $\mu\text{L}$ , and nodular liver surface on computed tomography scan or magnetic resonance imaging;
  - c. Clinical evidence of significant portal hypertension, based on current or history of gastroesophageal varices on endoscopy, evidence of portosystemic collaterals (on contrast computed tomography or magnetic resonance imaging with contrast), and/or presence of ascites;
  - d. Transient elastography consistent with cirrhosis, ie, a result of greater than 13.0 kPa.
4. A history of at least 1 or more documented episodes of HE within the last 12 months.
5. Hyperammonemia (defined as an ammonia level  $\geq 37 \mu\text{mol/L}$ ) at screening.
6. Currently using lactulose (minimum of 5 days prior to Day -1).
7. If using rifaximin at the Screening Visit, it must be discontinued at least 5 days before the first dose of study drug.
8. If female, be of non-childbearing potential (history of hysterectomy, bilateral oophorectomy, bilateral tubal ligation; or postmenopausal with no history of menstrual flow in the 12 months prior to the Screening Visit); or, if of childbearing potential, be non-pregnant, non-lactating and agree to use 2 forms of effective contraception when with a male partner for the duration of the study and for 28 days after any active treatment period. Acceptable forms of contraception include hormonal measures (oral contraceptive pills, contraceptive patch, contraceptive ring, injections), intrauterine devices, double barrier method (condom plus diaphragm, condom or diaphragm plus spermicidal gel or foam, surgical sterilization of the male partner), and abstinence.
9. If male with reproductive potential, agree to use 2 forms of effective contraception (abstinence, surgical sterilization [vasectomy], or condom with spermicide) with a female partner for the duration of the study and for 28 days after any active treatment period.

- 
10. Be able to communicate effectively with study personnel.
  11. Be able and willing to follow all protocol requirements and study restrictions.
  12. Be able and willing to return for all study visits.

## 5.2. Exclusion Criteria

A subject is ineligible for study participation if, at the Screening Visit, the subject:

1. Is from a vulnerable population, as defined by the US Code of Federal Regulations (CFR) Title 45, Part 46, Section 46.111(b) and other local and national regulations, including but not limited to, employees (temporary, part-time, full time, etc.) or a family member of the research staff conducting the study, or of the sponsor, or of the contract research organization, or of the Institutional Review Board (IRB)/Independent Ethics Committee (IEC).
  2. Has a history of sensitivity or allergy to MNK6106, ORN, PAA, L-ornithine L-aspartate, phenylbutyrate or rifaximin.
  3. Has expectation of liver transplantation within 1 month after the Screening Visit.
  4. Had placement of a portosystemic shunt or transjugular intrahepatic portosystemic shunt within 3 months before the Screening Visit.
  5. Has a Model for End Stage Liver Disease (MELD) score greater than 25.
  6. Has HESA score Grade 4.
  7. Had gastrointestinal bleeding within 3 months of the Screening Visit.
  8. Has severe renal impairment (Creatinine Clearance rate no more than 30 mL/min) calculated using the Cockcroft-Gault formula.
  9. Has intercurrent infection or active spontaneous bacterial peritonitis.
  10. Has known immune compromised status (not related to disease/condition under study), including but not limited to individuals who have undergone organ transplantation or who are known to be positive for the human immunodeficiency virus (HIV).
  11. Has any solid tumor malignancy currently diagnosed or undergoing therapy or has received therapy for any solid tumor malignancy in the 5 years prior to the Screening Visit; with the exception of treated and cured basal cell carcinoma, treated and cured squamous cell carcinoma of the skin, and treated and cured carcinoma in situ of the cervix.
  12. Has a history of prior cognitive impairment.
  13. Has a history of psychotic disorders including but not limited to schizophrenia, dementia, or other severe psychotic disorders that would interfere with evaluation of HE.
  14. Has a positive screening result for drugs and alcohol (except for subjects positive to cannabinoids).
-

- 
15. Has a QT interval corrected using Fridericia's Formula (QTcF) of at least 500 msec at screening.
  16. Has any of the following laboratory abnormalities at the Screening Visit:
    - Hemoglobin < 8.0 g/dL.
    - Platelet count < 25,000 cells/ $\mu$ L.
    - Absolute neutrophil count < 1000 cells/ $\mu$ L.
  17. Has any other clinically significant disease, disorder or laboratory abnormality, which, in the opinion of the investigator, might put the subject at risk due to participation in the study, or may influence the results of the study or the subject's ability to complete the study.
  18. Inability to swallow the study drug whole.
  19. Has hyponatremia, defined as blood sodium level  $\leq$  125 mmol/L.
  20. Is participating in or plans to participate in any other interventional research study from the time of screening and throughout this study.

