## CHANGES TO THE PROTOCOL

### Protocol Amendment 4 – Summary of Changes:

The primary purpose of Amendment 4 is to add 14 days to the screening period to give subjects more time to complete screening assessments due to extenuating circumstances of the COVID-19 pandemic. The changes to the protocol are listed below.

1. Section 1.2 Study Schematic: the following changes have been made:
    - a. Change: The Screening Visit from “Day -14 to Day -1” to read: “Day -28 to Day -1.”
    - b. Add footnote “a” to the table heading for Final Visit (7 days post-dosing) (+ 3 daya window) that reads: “If circumstances occur such that this visit cannot occur within the specified window, the visit window may be extended to 14 days, after discussion with the Sponsor.”
  2. Section 1.3 Schedule of Study Events: Change: Screening from “Day -14 to Day -1” to read: “Day -28 to Day -1.”
  3. Section 4.1 Overall Design:
    - 2nd paragraph, 2nd sentence: Change: “Subjects may participate in the study for a total of up to approximately 3 to 4 weeks, including a screening period of up to 14 days” to read: “Subjects may participate in the study for a total of up to approximately 6 weeks, including a screening period of up to 28 days.”
    - Add 3rd paragraph: “The final visit window may be extended, due to extenuating circumstances, to 14 days after discussion with the Sponsor.”
  4. Section 5.2: Add exclusion criterion #19: “Has hyponatremia, defined as blood sodium level  $\leq 125$  mmol/L.” Subsequent exclusion criterion renumbered accordingly.
  5. Section 5.4 Screen Failures:
    - 2nd paragraph: Change: “The period from the start of screening related procedures at the Screening Visit to randomization must not exceed 14 days, inclusive of any repeat screening procedures.” to read: “The period from the start of screening related procedures at the Screening Visit to randomization must not exceed 28 days, inclusive of any repeat screening procedures.”
    - 4th paragraph: Change: “Subjects may be rescreened for a subsequent episode of acute HE, provided that the subject was not randomized.” to read: Subjects may be rescreened provided that the subject was not randomized.
  6. Section 8.1 Screening:
    - Heading: Change: “Screening (Day -14 to Day -1)” to read: Screening (Day -28 to Day -1)”

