### 1.3. Schedule of Study Events

**Table 1: Schedule of Study Events**

Assessment/Procedure	Screening	Begin Confinement (Day -1)	Treatment Period (Days)					End Confinement (Day 6)	Final Visit (7 days post-dosing) (+ 3 day a window)
			1	2	3	4	5/ET		
Week			1						2
Day	-28 to -1	-1	1	2	3	4	5/ET	6b	12
Study Visit Number	1		2	3	4	5	6		7
Informed consent	X								
Inclusion/exclusion criteria review	X								
Child-Pugh (C-P) score	X		X	X	X	X	X	X	X
Model for End Stage Liver Disease (MELD) score	X		X	X	X	X	X	X	X
Conn score	X	X	X	X	X	X	X	X	X
Hepatic Encephalopathy Scaling Algorithm (HESA) score	X	X	X	X	X	X	X	X	X
Demographics	X								
Medical/surgical history (including history of exposure to COVID-19)	X								
Prior medication/therapies	X	X							
Complete physical examination	X	X							X

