## 4. STUDY DESIGN

### 4.1. Overall Design

This is a randomized, open-label, parallel group, multiple-dose, dose-ranging, active control, Phase 2a study. The objective of the study is to assess the PD, safety and PK of different doses of MNK6106 (oral administration) vs rifaximin in subjects 18 to 80 years of age (inclusive) with hepatic cirrhosis and a history of prior episodes of HE.

Approximately 48 subjects will be randomized to meet the primary objective. Subjects may participate in the study for a total of up to approximately 6 weeks, including a screening period of up to 28 days, a treatment period of 1 week (5 days), and a final visit 1 week (7 days [+ 3 day window]) after ending study treatment.

The final visit window may be extended, due to extenuating circumstances, to 14 days after discussion with the Sponsor.

Subjects will be confined to the study center overnight during the 5-day treatment period and randomly assigned to receive 1 of 3 dose regimens of MNK6106 or the comparator rifaximin for 5 days.

Approximately 48 subjects will be 1:1:1:1 randomized to 1 of the 4 groups. Subjects will receive either 1 of the 3 MNK6106 dosing regimens (2 g three times daily, 4 g twice daily, or 4 g three times daily) or rifaximin (550 mg twice daily) taken orally for 5 days. Samples for plasma AMM levels will be drawn at screening and on Days 1, 3 and 5/ET, predose in the morning immediately before breakfast and 4 hours ( $\pm$  15 minutes) after the morning dose as well as at the final visit. Samples for plasma PAA, ORN and PAGN will be drawn prior to the first dose on Day 1 (within 15 minutes prior to the morning dose) and then prior to (within 10 minutes) and 1 hour ( $\pm$  15 minutes) after the last dose on Days 1, 3, and 5/ET. Subjects will remain in the clinic overnight during Day 5/ET and be discharged on Day 6 after the last 24 hour urine collection is completed.

---

All treatment groups will be dosed orally as follows:

- Group A: MNK6106 2 g (2 tablets), three times daily for 5 days (6 g daily dose and 30 g total dose).
- Group B: MNK6106 4 g (4 tablets), twice daily for 5 days (8 g daily dose and 40 g total dose).
- Group C: MNK6106 4 g (4 tablets), three times daily for 5 days (12 g daily dose and 60 g total dose).
- Group D: Rifaximin 550 mg tablet (1 tablet), twice daily for 5 days (1.1 g daily dose and 5.5 g total dose).

Approximately 1 week after the end of the treatment period, subjects will complete a final visit.

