### **5.4. Screen Failures**

Screen failures are defined as subjects who consent to participate in the study but are not subsequently randomized.

The period from the start of screening related procedures at the Screening Visit to randomization must not exceed 28 days, inclusive of any repeat screening procedures.

Subjects who do not meet all of the eligibility criteria at the end of the screening period will be deemed a screen failure, and the following information must be recorded for all subjects who are screen failures:

- Demography (age, gender, race/ethnicity).
- Reason for screen failure.
- Eligibility criteria.
- Any AE/SAE experienced by the subject.

Subjects may be rescreened provided that the subject was not randomized. All Screening Visit procedures must be repeated.

Subjects may be rescreened only once. Subjects who are re-screened should not be assigned a new subject number. The original subject number should be retained.

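### Amendment 4 lengthened screening to 28 days, but the transplant exclusion still counts 1 month from the Screening Visit and can end on about Day 3; the timing of the eligibility check is also inconsistent across sections

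*Combined protocol and SAP*

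**What the plan says.** Exclusion 3 in section 5.2 applies to a subject who "Has expectation of liver transplantation within 1 month after the Screening Visit". The whole list is governed by its lead-in: "A subject is ineligible for study participation if, at the Screening Visit, the subject" meets any item. Section 5.1 opens with the same anchor for the inclusion criteria.

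Amendment 4 was written to "add 14 days to the screening period to give subjects more time to complete screening assessments". Its log shows that the superseded text of section 4.1 described participation "including a screening period of up to 14 days". The current text reads "Subjects may participate in the study for a total of up to approximately 6 weeks, including a screening period of up to 28 days".

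Table 1 has a row "Inclusion/exclusion criteria review" with one mark, in the Screening column (Day -28 to -1), and none in the Day -1 column.

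Two other places put the check later. Section 5.4 says "Subjects who do not meet all of the eligibility criteria at the end of the screening period will be deemed a screen failure". Section 8.2 has the inclusion and exclusion criteria confirmed before a subject begins the study. Section 6.3 randomizes only those who qualify on every criterion, and section 8.1 provides for replacing people found ineligible after screening.

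**The concern.** A forward-looking exclusion protects the study only for as long as its horizon lasts. When the clock starts at the Screening Visit and that visit may fall 28 days before dosing, most of a 1-month horizon can be spent before the first dose. A subject whose transplant is expected a few days into treatment, or between treatment and the Final Visit, can then pass exclusion 3 as written.

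The data at stake are the Day 5 ammonia samples, on which the primary outcome measure in section 3.3 rests, and the Final Visit sample and safety follow-up. With 48 subjects randomized 1:1:1:1 there are 48/4 = 12 per arm. Section 9.1 does not replace subjects who discontinue, and section 9.5.4 does not impute missing pharmacodynamic data. One lost subject is therefore 1/12, or about 8%, of an arm.

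The second part concerns uniformity between sites. Section 5 allows no waivers, so the wording decides who is eligible. If one section tests eligibility at the Screening Visit and another at the end of screening, two sites can reach different answers on the same subject, each with support in the text.

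**Working it through.** **Inputs**
- Screening: up to 28 days before Day 1 (4.1, 5.4, 8.1, Table 1); formerly up to 14 days (Amendment 4 log, used only to see what changed).
- Treatment: Days 1 to 5. Final Visit: 7 days (+3) after treatment, extendable to 14 days (4.1, 8.4).
- Exclusion 3 horizon: 1 month from the Screening Visit (5.2). The protocol does not define a month. I assume 30 days and show 28 to 31.
- Day numbering: Table 1 goes from Day -1 to Day 1, so there is no Day 0.

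**Reproducing the plan's own figures**
- Total participation: 28 + 5 + 7 = 40 days (5.7 weeks) to 28 + 5 + 10 = 43 days (6.1 weeks). This agrees with the stated 6 weeks.
- Final Visit: Day 5 + 7 = Day 12, as in Table 1; Day 5 + 10 = Day 15 at the end of the window; Day 5 + 14 = Day 19 if the extension runs from the last dose.
- Change in screening length: 28/14 = 2.0.

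**Day on which exclusion 3 runs out** (Screening Visit day + 1 month, no Day 0)

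| Screening on | 28 days | 30 days | 31 days |
|---|---|---|---|
| Day -28 (current limit) | Day 1 | Day 3 | Day 4 |
| Day -14 (former limit) | Day 15 | Day 17 | Day 18 |

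At the former limit, even the shortest month reached the end of the Final Visit window on Day 15. The shortfall therefore arrived with the 28-day window.

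**Earliest Screening Visit for which the horizon still reaches a given day**

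| Day to be reached | 28-day month | 30-day month | 31-day month |
|---|---|---|---|
| Day 5 | Day -24 | Day -26 | Day -27 |
| Day 12 | Day -17 | Day -19 | Day -20 |
| Day 15 | Day -14 | Day -16 | Day -17 |
| Day 19 | Day -10 | Day -12 | Day -13 |

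With a 30-day month, the horizon ends before Day 5 for screening on Day -28 or -27. It ends before Day 12 for screening on Day -28 to -20, which is 9 of the 28 permitted days.

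**Timing of the eligibility check, side by side**
- At the Screening Visit: lead-ins of 5.1 and 5.2; single mark in Table 1.
- At the end of screening, or before the subject begins: 5.4, 8.2.
- Collected on Day -1 (Table 1): Conn and HESA scores, complete physical examination, urinary drug screen, urine pregnancy test, concomitant medications and adverse events. No section says which of these findings excludes a subject.
- Not scheduled on Day -1: MELD, chemistry, hematology and ammonia. They recur on Day 1. The morning ammonia sample is predose; no timing relative to the first dose is given for chemistry, hematology or MELD.
- Exclusion 4 looks back from the Screening Visit, so as worded it does not reach a shunt placed afterwards.

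**The case against.** The best reply is that the protocol does confirm eligibility before dosing. A reader who looks only at the lead-ins and Table 1 might infer that acute exclusions such as infection are tied to no pre-dose check. The documents do not support that. Section 5.4 tests the criteria at the end of screening, 8.2 requires them to be confirmed before the subject begins (it is not limited to finishing the screening procedures), 6.3 randomizes only subjects who qualify on all criteria, and 8.1 foresees late ineligibility. Inclusions 6 and 7 run to Day -1 and the first dose, so eligibility is not wholly fixed at one early date.

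Nor does it follow that gastrointestinal bleeding after screening escapes every exclusion. Exclusion 7 is framed as within 3 months of the Screening Visit, not before it, and can be read to cover a later bleed. Exclusion 14 can likewise be read to include the Day -1 drug screen.

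The Screening Visit might also be read as the whole Day -28 to -1 column, which would ease the conflict with Table 1. But 5.4 measures up to 28 days from the start of procedures at that visit to randomization, and 8.1 repeats the pregnancy test on Day -1 because up to 28 days may have passed since screening. The broad reading would also leave exclusion 3 without a definite starting day.

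On the transplant horizon, Day 3 is the extreme case, and the documents give no frequency of expected transplants. Inclusion 12 (ability to attend every visit) and exclusion 17 (investigator's opinion on ability to complete the study) would catch some of these subjects. That stands in part: both are indirect and are judged at the same Screening Visit. Confirmation under 8.2 does not repair exclusion 3, because the criterion itself counts from that visit. Confirming it again on Day -1 gives the same end date.

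**Conclusion.** The point holds in two parts. First, exclusion 3 was not adjusted when screening was lengthened. Its cover can end on Day 3 (Day 1 to 4 across 28- to 31-day months), where it formerly reached Day 17 (Day 15 to 18). With a 30-day month, screening on 2 of the 28 permitted days leaves Day 5 outside the horizon, and screening on 9 of 28 leaves the Day 12 Final Visit outside it. These count permitted days; they are not probabilities, since the documents say nothing about when subjects will be screened or how many expect a transplant.

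Second, 5.1, 5.2 and Table 1 are not aligned with 5.4 and 8.2. This is an inconsistency about when the criteria apply and which Day -1 findings count. It is not the absence of a pre-dose check.

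The study is exploratory, with no hypothesis test and no power calculation, so neither the sample size nor an error rate is affected. The change is worth making because it protects Day 5 data in small arms and makes eligibility uniform between sites.

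**What to change.** 1. **Exclusion 3.** Re-anchor the horizon so that it spans the subject's participation through the Final Visit, as it did under the 14-day window. As an arithmetic illustration only, 1 month counted from Day 1 would end on Day 31 (range Day 29 to 32), past both Day 15 and an extended Final Visit on Day 19.
2. **Timing of eligibility.** Reconcile the lead-ins of 5.1 and 5.2 and Table 1 with 5.4 and 8.2. Add a mark for eligibility review in the Day -1 column, limited to interval history and the HESA, Conn, physical examination and drug-screen results already collected that day, and state which of these findings exclude a subject. State also whether a shunt placed between the Screening Visit and Day -1 falls under exclusion 4.
3. **Laboratory-based criteria.** Do not extend the lead-ins to MELD, sodium, creatinine clearance or ammonia on Day -1. Those tests are not scheduled then, and Amendment 3 clarified that Child-Pugh and MELD need not be repeated at confinement. The sponsor should instead state whether Day 1 values count toward eligibility.

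The cost is amendment wording and one mark in Table 1, with no new procedure as long as item 3 is respected. The downside is that a few more subjects will be screened out on Day -1.

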### **5.3. Lifestyle Considerations**

Subjects should not donate blood or plasma for the duration of this study and for 28 days after study exit.

Subjects will be instructed to refrain from strenuous exercise from 48 hours prior to randomization through to 24 hours after the final PK sample is taken.

### **5.4. Screen Failures**

Screen failures are defined as subjects who consent to participate in the study but are not subsequently randomized.

The period from the start of screening related procedures at the Screening Visit to randomization must not exceed 28 days, inclusive of any repeat screening procedures.

Subjects who do not meet all of the eligibility criteria at the end of the screening period will be deemed a screen failure, and the following information must be recorded for all subjects who are screen failures:

- Demography (age, gender, race/ethnicity).
- Reason for screen failure.
- Eligibility criteria.
- Any AE/SAE experienced by the subject.

Subjects may be rescreened provided that the subject was not randomized. All Screening Visit procedures must be repeated.

Subjects may be rescreened only once. Subjects who are re-screened should not be assigned a new subject number. The original subject number should be retained.

## 6. STUDY TREATMENT

Study treatment is defined as any investigational treatment, marketed products, placebo, or device intended to be administered to a study subject according to the study protocol. Subjects enrolled in this study will receive study treatment under open-label conditions.

The study treatments will be dispensed by the investigator or investigator's designee. The treatment groups, frequency and dose are summarized in [Table 2](#).

